- Section 7.1.6- Discontinuation of study treatment: The criteria for study treatment discontinuation “documented lack of efficacy, disease progression” was removed. All patients (excluding patients that died, withdrew consent or are lost to follow-up), are followed up for survival after the treatment phase.
- Section 7.1.6- Discontinuation of study treatment: clarification added to distinguish between discontinuation of study treatment versus discontinuation of study.
- Section 7.2.2.1- Physical examination: clarification of methodology to assess extramedullary involvement.
- [REDACTED]
- Section 7.2.6- Patient reported outcomes: The statement “The original questionnaire will be kept with the patient’s file as the source document.” was removed. Questionnaires will be completed electronically; no paper copies will be kept in the source documents.
- Section 10.1.5- Pharmacokinetic analysis set: The number of consecutive days required for PK concentration evaluability was corrected to “3” days. ABL001 should be taken at least 3 consecutive days without interruption or dose modification prior to full PK day.

IRBs/IECs

A copy of this amended protocol will be sent to the Institutional Review Board (IRBs)/Independent Ethics Committee (IECs) and Health Authorities.

The changes described in this amended protocol require IRB/IEC approval prior to implementation.

The changes herein affect the Informed Consent. Sites are required to update and submit for approval a revised Informed Consent that takes into account the changes described in this protocol amendment.

2. Statistical Analysis Plan

Clinical Development

ABL001/asciminib

CABL001A2301

A phase 3, multi-center, open-label, randomized study of oral ABL001 versus bosutinib in patients with Chronic Myelogenous Leukemia in chronic phase (CML-CP), previously treated with 2 or more tyrosine kinase inhibitors

Statistical Analysis Plan (SAP)

Author: Statistician, [REDACTED]

Document type: SAP Documentation

Document status: Final

Release date: 25-Aug-2017

Number of pages: 53

Document History – Changes compared to previous final version of SAP

Date	Time point	Reason for update	Outcome for update	Section and title impacted (Current)
25-Aug-2017	Prior to DB lock for primary analysis	Creation of final version	N/A - First version	NA

Table of contents

Table of contents	3
1 Introduction	7
1.1 Study design.....	7
1.2 Study objectives and endpoints	8
2 Statistical methods.....	9

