For efficacy evaluations, the last non-missing assessment, including unscheduled assessments on or before the date of randomization is taken as “baseline” value or “baseline” assessment. In the context of baseline definition, the efficacy evaluations also include PRO and performance status.

For safety evaluations, the last available assessment on or before the date of start of study treatment is taken as “baseline” assessment.

For pre-dose electrocardiogram (ECG), the last available assessment before the treatment start date/time is used for baseline.

For ECGs, where study requires multiple replicates per time point, the average of these measurements would be calculated for baseline (if not already available in the database).

In rare cases where multiple laboratory measurements meet the baseline definition, with no further flag or label that can identify the chronological order, then the following rule should be applied: If values are from central and local laboratories, the value from central assessment should be considered as baseline.

If patients have no value as defined above, the baseline result will be missing.

On-treatment assessment/event and observation periods

For adverse event reporting the overall observation period will be divided into three mutually exclusive segments:

1. ***pre-treatment period***: from day of patient’s informed consent to the day before first administration of study treatment
2. ***on-treatment period***: from date of first administration of study treatment to 30 days after date of last actual administration of any study treatment (including start and stop date). Note: Patients will be treated for up to LPFT + 96 weeks. This will be the last actual administration of study treatment for each patient if the patient has not discontinued study treatment earlier. After this period, the assigned study treatment will be made available, may be outside of this study, to patients who in the opinion of the investigators are still deriving clinical benefit.
3. ***post-treatment period***: starting at day 31 after last administration of study treatment.

If dates are incomplete in a way that clear assignment to pre-, on-, or post-treatment period cannot be made, then the respective data will be assigned to the on-treatment period.

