26-Mar-2020	Prior to DB lock for primary analysis	Implementation of protocol amendments 2 and 3. Additional analyses, clarification	
ABL001 has been replaced by International Nonproprietary Name (INN) asciminib.
 
Introduction of the switch to asciminib option for patients experiencing treatment failure on bosutinib treatment
 
Update of the definition of end of study treatment
 
Added a potential End-of-Study-Treatment analysis different from the 96-week analysis
 
Addition/removal of secondary safety objectives and exploratory efficacy objectives
 
Clarification on which data are included in the analyses, which assessments are considered for safety and efficacy analyses
 
Addition of the treatment arms and definition of the date of end of study treatment Removal of windows defined for ECGs, LVEF and PK assessments as they are not needed.
	
Throughout the SAP amendment
 
Section 1.1, Figure 1-1 Sections 2.1, 2.3 Analyses added throughout the document Section 1.1
 
Table 1-1
 
Section 2.1
 
Section 2.1.1

As per Health Authorities request, addition of the breakdown per different time points of the number (%) of patients who discontinued the study treatment phase and of the primary reason for study treatment phase discontinuation

Section 2.3.1

PAS: Removal of the condition related to vomiting to consider a concentration evaluable as the occurrence and time of vomiting is not collected in the CRF.

Section 2.2

Addition of a subgroup “Stratum reported in the CRF” for the analysis by subgroup of the primary endpoint (to take into account the mistratification cases)

Section 2.2.1

Removal of the subgroup “with or without historical BCR-ABL1 mutation by local lab” as this is not considered clinically relevant

Additional analyses of prior TKI and non TKI antineoplastic therapies

Section 2.4.2

Implementation of the estimand language for the primary and key secondary objectives

Sections 2.5 and 2.6

Addition of a sensitivity analysis of the primary estimand stratifying by the stratum recorded in the CRF to take into account that many stratification errors occurred

Section 2.5.5

Addition of Time-to-event analyses for time to MMR and time to CCyR

Section 2.7.2

			Added how time is censored for time to MMR/CCyR, clarification on how to handle missing BMA assessments due to MMR being achieved	Section	2.7.3

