2. **on-treatment period:** from date of first administration of study treatment to 30 days after date of last actual administration of study treatment (including start and stop date) (LD). Note: Patients will be treated up to the end of study treatment period (EOsT). This will be the last actual administration of study treatment for each patient if the patient has not discontinued study treatment earlier. On this date, all patients without treatment switching will have been treated for at least 96 weeks unless patients have discontinued study treatment earlier. After this period, the assigned study treatment will be made available, may be outside of this study, to patients who in the opinion of the investigators are still deriving clinical benefit.
3. **post-treatment period:** starting at day 31 after last administration of study treatment.

For subjects with treatment switching from bosutinib to asciminib:

- **pre-treatment period:** from day of patient's informed consent to the day before first administration of study treatment (FD)
- **on-treatment period:** from date of first administration of study treatment to either the day before the first administration of asciminib (FD_{switch}) or 30 days after the date of last actual administration of bosutinib (LD), whichever comes first.
- **post-treatment period:** from day 31 after last administration of bosutinib to the day before the first administration of asciminib (FD_{switch}). If the end date is before the start date, this period is not applicable.
- **on-switched treatment period:** from date of first administration of asciminib (FD_{switch}) to 30 days after date of last actual administration of asciminib (LD_{switch}).
NOTE: Subjects are treated in the study up to end of study treatment period (EOsT). On this date, all subjects with treatment switching will have been treated for at least 48 weeks after switching unless they have discontinued the switched treatment earlier.
- **Post-switched treatment period:** from day 31 after last actual administration of asciminib (LD_{switch}).

If dates are incomplete in a way that clear assignment to pre-, on-, post-, on-switched-, post-switched-treatment period cannot be made, then the respective data will be assigned to the on-treatment period.

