of prior applicable visit" +1. "Upper limit" = "target day of current visit" + integer part of ("target day of next applicable visit" – "target day of current visit")/2.

Visit window for the switched treatment period will use the same rules as described above but with Day 1 being the date of first administration of asciminib. Visit name for the switched treatment period will be defined similarly with annotated by beginning with "S-" (e.g. S-Week 4) to differentiate from those used for the randomized treatment period.

Last contact date

The last contact date will be derived for patients not known to have died at the respective analysis data cut-off date using the last complete date among the following:

Table 2-5 Last contact date data sources

Source data	Conditions
Date of randomization	No condition
Last contact date/last date patient was known to be alive from Survival Follow-up page	Patient status is reported to be alive, lost to follow-up or unknown
Start/End dates from further antineoplastic therapy	Non-missing medication/procedure term
Start/End dates from drug administration record	Non-missing dose. Doses of 0 are allowed
End of treatment date from end of treatment page	No condition
Any specific efficacy (molecular or cytogenetic) assessment date if available	Evaluation is marked as 'done'
Laboratory/PK collection dates	Sample collection marked as 'done'
Vital signs date	At least one non-missing parameter value
Performance status date	Non-missing performance status
Start/End dates of AE	Non-missing verbatim term

The last contact date is defined as the latest complete date from the above list on or before the respective data cut-off date. The cut-off date will not be used for last contact date, unless the patient was seen or contacted on that date. No date post the cut-off date will be used. Completely imputed dates (e.g. the analysis data cut-off date programmatically imputed to replace the missing end date of a dose administration record) will not be used to derive the last contact date.

The last contact date will be used for censoring of patients in the analysis of overall survival.

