2.4.2 Prior, concomitant and post therapies

Prior anti-cancer therapy

The number and percentage of patients who received any prior anti-neoplastic medications will be summarized by treatment arm for the lowest anatomical therapeutic classification (ATC) class and preferred term. A listing will also be produced.

Anti-neoplastic medications will be coded using the WHO Drug Dictionary (WHO-DD). Details regarding WHO-DD version will be included in the footnote in the tables/listings.

The above analyses will be performed using the FAS.

The following information will be summarized for the FAS and Switch Analysis Set:

- Prior TKI by medication (e.g. imatinib, dasatinib, nilotinib, ponatinib, bosutinib, etc.)
- Number of prior TKI (e.g. 2, 3, 4, etc.)
- Number of lines of prior TKI therapy (2, 3, 4, 5+)
A new line of therapy is considered each time a change in TKI occurred. Multiple entries for the same TKI will be counted as separate lines of therapy if a different TKI is received between the different entries.
- Time on each line of prior TKI therapy (in years)
- Time on last prior TKI (in years)
- Reason to discontinue the most recent TKI therapy at the time of screening
- Prior non-TKI therapies (Yes, No).

A Sankey-like plot showing the sequence of prior TKIs will be provided.

Note: In case the last TKI given prior to enrollment in the study was a bridging therapy (i.e. reason for discontinuation includes a wording related to bridging), it will not be considered in the analysis of prior TKIs. In particular, it will not be considered as the last or most recent TKI therapy at the time of screening and will not count as an additional line of therapy.

For the Switch Analysis Set, bosutinib received during the randomized treatment period and other TKIs received since discontinuation of bosutinib and before first administration of asciminib (FD_{switch}) should be considered as prior TKIs.

Post treatment anti-cancer therapy

Anti-neoplastic therapies since discontinuation of study treatment will be listed and summarized by the lowest anatomical therapeutic classification (ATC) class, preferred term, overall and by treatment group by means of frequency counts and percentages using FAS.

Anti-neoplastic medications will be coded using the WHO-DD. Details regarding WHO-DD version will be included in the footnote in the tables/listings.

Concomitant therapies

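### In the current SAP only the bosutinib-to-asciminib switch ends the on-treatment period early, so all-causality safety tables handle events after the next TKI differently by arm; the size and net direction are unknown

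*Combined protocol and SAP*

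**What the plan says.** The first SAP ("Release date: 25-Aug-2017") has no switch option and applies one 30-day rule to everyone: "from date of first administration of study treatment to 30 days after date of last actual administration of any study treatment". The SAP document history for 26-Mar-2020 then records the "Introduction of the switch to asciminib option for patients experiencing treatment failure on bosutinib treatment".

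The latest SAP reproduced in full (document history to 14-Oct-2020) has separate definitions in section 2.1.1:

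- **Patients who do not switch, either arm:** the on-treatment period runs "from date of first administration of study treatment to 30 days after date of last actual administration of study treatment".
- **Bosutinib patients who switch:** it ends at "either the day before the first administration of asciminib" or 30 days after the last bosutinib dose, whichever comes first.
- **Switch phase:** the period starts with first asciminib and runs to 30 days after LD_switch.

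None of the three ends when some other antineoplastic therapy starts. Such therapy is recorded, however. Section 2.4.2 states: "Anti-neoplastic therapies since discontinuation of study treatment will be listed". Table 2-5 draws on "Start/End dates from further antineoplastic therapy" for the last contact date.

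Section 2.1.1 limits safety summaries to on-treatment (or on-switched) data. Sections 2.8.1 (AEs), 2.8.2 (on-treatment deaths) and 2.8.3 (worst laboratory grades) follow that window.

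**The concern.** Comparing safety and tolerability between arms is a secondary objective (Table 1-1). Take two patients whose treatment fails and who start a new drug on day 7 after the last dose. The asciminib patient cannot switch within the study, so days 7 to 30 stay in the asciminib column although another TKI is being taken. The bosutinib patient who switches to asciminib has none of those days in the bosutinib column. The same sequence is counted in two ways, and one of them is open to one arm only.

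The tables exposed are the all-causality ones: treatment-emergent AEs, worst laboratory grades where samples exist, and on-treatment deaths. The switch-phase summaries have the same uncut tail, and they serve a further secondary objective, the safety of asciminib after bosutinib failure.

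**Working it through.** The plan gives no figure to reproduce, so the check is of the definitions, followed by an illustration.

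**1. What ends the period (current section 2.1.1)**

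| Patient | Last dose + 30 days | First asciminib in the switch phase | Any other new antineoplastic |
|---|---|---|---|
| Asciminib arm | yes | not available | no |
| Bosutinib arm, no switch | yes | not applicable | no |
| Bosutinib arm, switch | yes | yes, if earlier | no |
| Switch phase | yes (LD_switch) | not applicable | no |

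The cut is at asciminib, not at whichever drug comes next. Section 2.4.2 foresees TKIs taken after bosutinib is stopped and before asciminib begins, and these do not end the period. For example (assumed days), another TKI from day 5 and asciminib from day 20 leaves days 5 to 19, that is 15 days, on a third drug inside the bosutinib period.

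**2. Days on another drug inside the window**

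Let g be the day after last dose on which the next drug starts, and s the share of switchers among bosutinib patients who start another drug. Both are assumptions, because the documents give neither. Take g as equal in the two arms and switchers as going straight to asciminib.

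- Non-switcher: D = 30 − g + 1. Direct switcher: 0.
- Bosutinib average: D × (1 − s). Gap between arms: D × s.

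| g | Asciminib (D) | Bosutinib, s = 0.25 | Bosutinib, s = 0.5 | Gap, s = 0.5 |
|---|---|---|---|---|
| 1 | 30 | 22.5 | 15 | 15 |
| 7 | 24 | 18 | 12 | 12 |
| 14 | 17 | 12.8 | 8.5 | 8.5 |
| 28 | 3 | 2.2 | 1.5 | 1.5 |

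At s = 0 the gap is 0 for every g. These are days per patient who starts another drug, not event rates.

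**3. Net direction over whole arms**

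Let p_A and p_B be the proportions of each arm that stop and start another drug. The tail then affects p_A of the asciminib arm and p_B × (1 − s) of the bosutinib arm. Two assumed cases with s = 0.5:

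- p_A = 0.20, p_B = 0.50: 20% against 0.50 × 0.5 = 25%. More of the bosutinib arm is affected.
- p_A = p_B = 0.30: 30% against 0.30 × 0.5 = 15%. More of the asciminib arm is affected.

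The direction turns on whether p_A exceeds p_B × (1 − s), and the documents supply none of the three.

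**4. Laboratory window**

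Section 2.8.3 admits all assessments up to 30 days after the last study treatment and does not repeat the switch cut, while its worst-grade summary refers to the on-treatment period. For a switcher the two limits differ whenever asciminib starts within 30 days of last bosutinib.

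**The case against.** The strongest reply is that the switch cut was never meant as a next-drug rule. Section 2.1.1 divides a switcher's follow-up into non-overlapping periods, and asciminib in the switch phase is itself a study treatment with its own tables. Without the cut one event could fall in two periods. Other patients have no second study-treatment period to separate. This stands as an explanation of the rule, and it means that extending the cut would be a new rule for switchers too. It does not make the arm comparison like for like.

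Second, an all-causality window of last dose + 30 days is a defensible choice that retains late study-drug toxicity, and the primary database lock has passed. This also stands, and it argues against replacing the main tables.

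Third, part of the issue is already visible. AEs are also tabulated by relationship, which depends on the relationship recorded for each event, and deaths are shown both on-treatment and overall. The protocol amendment log allows the safety follow-up visit by telephone, so few laboratory samples or ECGs may fall in the tail. The point is therefore confined to all-causality tables and may matter little for laboratory data.

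Fourth, the text reviewed does not include the main protocol body or the body of any later SAP. A rule there on AE collection after new therapy cannot be excluded.

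A reader might go further and infer that the rule makes asciminib look worse, perhaps by a stated number of points. Multiplying an assumed share starting another TKI, an assumed chance of first onset in the tail and an assumed 85% without an earlier event gives 0.2 × 0.1 × 0.85 = 1.7 to 0.4 × 0.4 × 0.85 = 13.6 percentage points. None of those inputs is in the documents. The product also sets the whole asciminib arm against bosutinib switchers alone, although bosutinib patients who stop without switching keep the same 30-day tail. In addition, the cut moves any late bosutinib events in switchers into the switch phase.

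**Conclusion.** The asymmetry of the rule follows directly from section 2.1.1: a cut at the next drug exists for one kind of transition, which only one arm can make, and no analysis in the text reviewed removes the difference. Its effect is not established. The average gap of 0 to 15 days on another drug, per patient who starts one, rests on assumed start days of 1 to 28 after last dose and an assumed switch share of 0 to 50%. It cannot be turned into a difference in event rates, and the net direction over whole arms cannot be given. The 2017 SAP does not have the defect, since it treats both arms alike. The primary efficacy test is unaffected. A parallel set of tables is a cheap improvement; replacing the main safety window is not called for.

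**What to change.** For the 96-week and end-of-study-treatment analyses:

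1. Keep the existing tables based on last dose + 30 days.
2. Beside them, add the main AE, laboratory and on-treatment death summaries with the period ended, for every patient in both arms and in the switch phase, at the earlier of 30 days after last dose (LD, or LD_switch in the switch phase) and the day before the first dose of any new antineoplastic therapy. A TKI taken between bosutinib and asciminib counts as new therapy. Use the start dates already collected (section 2.4.2, Table 2-5).
3. Reconcile the 30-day laboratory limit in section 2.8.3 with the switch cut in section 2.1.1.

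The cost is some SAP wording, one extra derivation and one extra table set, which must be labelled as added after the primary database lock. The truncated tables leave out late study-drug events that begin after the new therapy; the retained tables still show them.

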2.2 Analysis sets

Full Analysis Set

The Full Analysis Set (FAS) comprises all patients to whom study treatment has been assigned by randomization. According to the intent to treat principle, patients will be analyzed according to the treatment and stratum they have been assigned to during the randomization procedure.

Per Protocol Set

The Per-Protocol Set (PPS) consists of a subset of the patients in the FAS who are compliant with requirements of the clinical study protocol (CSP). The PPS will be used for sensitivity analyses on the primary endpoint only.

The following list of protocol deviations will lead to exclusion of the patient from the PPS:

- Type of indication different from those required by the CSP, e.g., not CML-CP, BCR-ABL ratio <1% International Scale (IS), with T315I or V299L mutation (INCL03, INCL04, INCL05, EXCL01)
- If prior therapy does not match with CSP requirements in terms of number and types of previous therapy regimens (INCL06)
- Study treatment received different from treatment assigned by randomization (TRT08)

Safety Set

The **Safety Set** includes all subjects who received at least one dose of study treatment. Subjects will be analyzed according to the study treatment actually received.

The actual treatment received corresponds to:

- the randomized treatment if patients took at least one dose of that treatment;
- the first treatment received if the randomized treatment was never received.

Pharmacokinetic Analysis Set

The **Pharmacokinetic Analysis Set (PAS)** includes all patients who provide at least one evaluable PK concentration. For a concentration to be evaluable, patients are required to:

- Take a dose of ABL001 prior to sampling
- Take the same dose of ABL001 for at least 3 consecutive days without dose interruption or dose modification prior to sampling
- For pre-dose samples, do not vomit within 4 hours after the dosing of ABL001 prior to sampling (this is the previous dose); for post-dose samples, do not vomit within 4 hours after the dosing of ABL001 (this is the current dose)
- Have the pre-dose sample collected before the next dose administration

Other analysis sets

- For duration of MMR and time to MMR, the **MMR Responder Set** will be used that is a subset of FAS and includes patients who achieve MMR at any time on study treatment.
- For CCyR rates at and by scheduled time points, the **CCyR Analysis Set** will be used that is a subset of FAS and includes patients who are not in CCyR at baseline.
- For duration of CCyR and time to CCyR, the **Cytogenetic Responder Set** will be used that is a subset of FAS and includes patients who do not have CCyR at baseline and achieve CCyR at any time on study treatment.

Patient Classification

Patients may be excluded from the analysis populations defined above based on the protocol deviations entered in the database and/or on specific subject classification rules defined in [Table 2-9](#).

Table 2-9 Subject classification based on protocol deviations and non protocol deviation criteria

Analysis set	Protocol deviations leading to exclusion	Non protocol deviation leading to exclusion
FAS	No written inform consent	Not applicable
Safety set	No written inform consent	No dose of study medication
Per-protocol set	See definition of PPS	Another anti-neoplastic therapy administered after start of study treatment
PK analysis set	No written inform consent	See definition of PAS
MMR Responder Set	Not applicable	See definition of MMR Responder Set
CCyR Analysis Set	Not applicable	See definition of CCyR Analysis Set
Cytogenetic Responder Set	Not applicable	See definition of Cytogenetic Responder Set

Withdrawal of Informed Consent

Any data collected in the clinical database after a subject withdraws informed consent from all further participation in the trial, will not be included in the analysis. The date on which a patient withdraws full consent is recorded in the eCRF.

